1.1.2 Hypotheses / Research Questions

Hypothesis 1: Greater than 70% of caregivers will perceive the checklist to be an acceptable length and easy to use.

Hypothesis 2: Greater than 70% of caregivers will report that the checklist is helpful in identifying their unmet needs and starting a discussion with providers.

Hypothesis 3: Greater than 70% of caregivers and providers will report that they desire to continue using the checklist in the future.

Hypothesis 4: The checklist will not significantly impact primary care workflow or visit duration.

Hypothesis 5: Discussion of caregivers' needs and concerns will occur more often in the intervention group than in the usual care group.

Hypothesis 6: Caregiver perceptions of visit communication will be more positive in the intervention group than in the usual care group.

2. Background and Significance

In the United States, nearly 8 million older adults rely on family and other unpaid caregivers (neighbors; friends) for assistance with their health care. These caregivers collectively provide 75-80% of the total care hours to community-dwelling older adults and fill multiple roles in the health care system: attending doctor's visits, coordinating care, and assisting with treatment regimens. The availability and adequacy of assistance provided by family and unpaid caregivers have direct implications for health care costs and quality of care of older adults. Yet, caregivers are not systematically identified in care delivery systems, and their abilities and needs are not routinely assessed. Caregivers receive inadequate preparation for the tasks they must assume. They report high levels of stress and are at risk for physical illness, depression and anxiety, and sleep disturbance. If these impairments and unmet needs are not assessed and addressed, they can impede the caregiver's ability to provide effective assistance to the older adult, ultimately leading to costly hospitalizations and nursing home placements. These caregiver factors (health impairments; unmet needs) are particularly influential in the context of dementia where patients require substantial caregiving assistance.

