3.1 Overall Design

Clinicians who see patients at the Center on Aging (COA) will be made aware of the study via individual meetings with co-investigators. These meetings will be by phone, Zoom, or in-person if/when feasible. Patients and caregivers will be identified through referrals from physicians practicing at the Center on Aging. They will be sent a recruitment letter in the mail one month prior to a co-investigator calling them to go over the screening and consent forms. Any study data collected for potential participants that do not meet eligibility will be immediately deleted. Informed Consent and HIPAA authorization for caregivers and patients, and informed consent for clinicians will occur orally over the phone or in-person at the COA just prior to in-person health visits when feasible as outlined in the Informed Consent section.

Patient-caregiver dyads will be randomized into either the CHEC (n=60; 30 caregivers and 30 patients) or control (usual care) condition (n=60; 30 caregivers and 30 patients). Randomization will occur through block randomization with alternative block sizes of 4 and 6 for each participating clinician.

Intervention Condition. Participants in the intervention condition will complete the Caregiver Checklist portion of CHEC at the beginning of their health visit. The participating clinician will then respond to the checklist following the guidelines on the accompanying Tip Sheet.

Control Condition. Caregivers in the control condition will receive their usual care from the participating clinician during the health visit.

Baseline (pre-visit). Caregivers in both conditions will be asked to complete identical pre-visit surveys. The survey will be scheduled to be completed over the phone, digitally on REDCap, or in-person depending on the participant's preference and COVID-19-related guidelines. We will ask about the participant's background, caregiving role, communication with providers, and feelings of caregiver preparedness. It will take approximately 20 minutes to complete. Medical chart abstraction will be used to collect patient's background characteristics, medications, diseases, and health events (e.g., hospitalization). Clinicians will complete a pre-intervention survey over the phone or in-person depending on the participant's preference and COVID-19-related guidelines. We will ask for the clinicians' personal characteristics and preparedness to assess and address caregivers' needs and concerns.

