- Patient data will be abstracted from the medical chart. Information obtained will include name, address, phone number, age, gender, race/ethnicity, provider, MRNs, electronic mail addresses and health diagnosis information including primary visit diagnosis code and clinic location (from defined time window), and health events (e.g. hospitalization, visit from home health aide). A partial HIPAA waiver will be requested for access to this information. All participants will be provided with a participant ID and their survey responses will be de-identified. Records will be maintained and kept in secure locations for a minimum of 3 years; the length of time specified according to WCM and HIPAA policies.

B. Study Instruments

The primary instruments for this study are validated, widely-used patient- and caregiver-reported outcomes (PCRO) assessments that are commonly used in health services research and clinical practice. These validated and reliable self-report measures include: Preparedness for Caregiving scale (Zwicker, 2010), CAPACITY measure (Van Houtven et al., 2019), Perceptions of Visit Communication (Talen et al., 2011), Caregiver Satisfaction with Primary Care Interactions (Clair et al., 2014; Haley et al., 1992), Perceived Self Efficacy in Primary Care Interactions (Maly et al., 1998), knowledge and use of resources (Thomas et al., 2017), caregiver anxiety and depressive symptoms (Mauer, 2012; Wild et al., 2014), and burden (Zarit, Reever & Bach-Peterson, 1980). We will use short forms when possible in order to reduce participant burden. We also developed several specific questions about caregivers' perception of the screening tool and knowledge of resources. All study instruments are attached to the IRB application in the WRG-HS system.

- Caregiver Subjects in CHEC (intervention group)

- CHEC Caregiver Screening Questions
- CHEC Caregiver Demographics
- CHEC Caregiver Pre-Test Questionnaire

- CHEC Visit Companion Checklist
- CHEC Caregiver 1-Week Post-Test Follow-Up Survey – Intervention
- CHEC Caregiver 2-Month Post-Test Follow-Up Survey – All Caregivers
- CHEC Caregiver 6-Month Post-Test Follow-Up Survey – All Caregivers
- Caregiver Subjects in control group
 - CHEC Caregiver Screening Questions
 - CHEC Caregiver Demographics
 - CHEC Caregiver Pre-Test Questionnaire
 - CHEC Caregiver 1-Week Post-Test Follow-Up Survey – Control
 - CHEC Caregiver 2-Month Post-Test Follow-Up Survey – All Caregivers

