7.2.5 Record Retention

Essential documents are those documents that individually and collectively permit evaluation of the study and quality of the data produced. After completion of the study, all documents and data relating to the study will be kept in an orderly manner by the Investigator in a secure study file. Essential documents should be retained for 2 years after the final marketing approval in an ICH region or for at least 2 years since the discontinuation of clinical development of the IP. In addition, all subject medical records and other source documentation will be kept for the maximum time permitted by the hospital, institution, or medical practice.

8. Statistical Considerations

Feasibility and acceptability will be examined by conducting frequency and descriptive statistics (i.e. mean, median, standard deviation, range) for enrollment rates and Likert-scale items assessing satisfaction with CHEC and perceived helpfulness.

Effectiveness will be measured by the number of completed checklists that result in a conversation with providers about caregiver needs and the receipt of relevant support. The effect of CHEC on the primary outcome variable, discussion of caregivers' needs, will be examined in a general linear mixed model with intervention group and time (pre-posttest) as fixed classification

factors, and individuals as levels of a random classification factor. The model will account for pre-intervention measures and will include a group x time interaction. Additional covariates (e.g., caregiver and care recipient age) and fixed classification factors (e.g., caregiver gender, race) will also be examined. Prior to model fitting, the distribution of all study variables will be assessed.

9. Adverse Event Reporting Requirements

Adverse event (AE) monitoring and reporting is a routine part of clinical research. Safety is monitored by evaluation of adverse events reported by subjects or observed by investigators or research staff, as well as by other investigations such as clinical laboratory tests, x-rays, electrocardiographs, etc.

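### Section 8 fixes no covariate set for the comparison of caregiver-needs discussion (Hypothesis 5) and leaves out clinician, the factor within which randomisation is blocked

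*Combined protocol and SAP*

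**What the plan says.** Section 8 (Statistical Considerations) states that discussion of caregivers' needs "will be examined in a general linear mixed model with intervention group and time (pre-posttest) as fixed classification" factors, with individuals as a random factor. It continues: "The model will account for pre-intervention measures and will include a group x time interaction". The covariate sentence is: "Additional covariates (e.g., caregiver and care recipient age) and fixed classification factors (e.g., caregiver gender, race) will also be examined". The pre-intervention measures are not identified, and nothing says which covariates stay in the reported model or how that is decided. Clinician does not appear.

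Section 3.1 assigns 30 dyads to each arm by blocks of 4 and 6 within each participating clinician. No other factor is balanced by design.

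On patient cognition, Section 2 says of caregivers: "These caregiver factors (health impairments; unmet needs) are particularly influential in the context of dementia where patients require substantial caregiving assistance". A later paragraph of Section 2 says that caregiver needs change with the patient's physical health and cognitive function. Section 3.1 states: "Medical chart abstraction will be used to collect patient's background characteristics, medications, diseases, and health events (e.g., hospitalization". Section 3.2 adds "health diagnosis information including primary visit diagnosis code and clinic location (from defined time window" and times the abstraction after consent and before the visit. Section 4.2 lets patients enrol through a legal representative, so cognitive status will probably vary in the sample.

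**The concern.** There are two separate gaps.

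First, if covariates are examined on the outcome data with no rule, several defensible estimates of the arm difference exist and the plan does not say which one is the result. With 60 dyads these estimates can differ by several percentage points, which matters in a pilot meant to give a preliminary effect.

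Second, blocking within clinician removes clinician differences from the arm comparison. An analysis that ignores clinician leaves those differences in the residual variance. The standard error is then too large, and precision that the design bought is not used.

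The example covariates are all demographic. The patient characteristics that Section 2 links to changing caregiver needs are physical health and cognitive function, and the pre-visit chart abstraction should make a cognitive diagnosis available. That makes it a reasonable candidate for a fixed model.

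**Working it through.** The documents give no alpha, event rate, effect size, power or dementia prevalence, so there is no planned figure to reproduce. The inputs taken from them are 60 dyads, 30 per arm; up to 10 clinicians, about 60/10 = 6 dyads each; and four named covariates (caregiver age, patient age, caregiver gender, race). Everything else below is assumed: two-sided 5% tests and a linear model on one yes/no outcome per dyad.

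**1. Choosing among covariate sets.** Four covariates give 2^4 = 16 models. In null simulations with 60 dyads, the share of trials in which at least one model gave p < 0.05 was:
- 7.1% at a 45% discussion rate with covariates unrelated to outcome (5,000 runs), against 5.2% for the unadjusted model;
- between 6.7% and 10.5% at a 35% rate, over repeated simulations with three covariate strengths each. Fixed linear models rejected in about 4.5-5.6%.

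With a fifth covariate (2^5 = 32 models) the share was 8.6% if it was unrelated to outcome and 9.6% if it shifted the rate by 30 points. Across models, the estimated arm difference ranged over a median of 4-7 points and a 90th percentile of 8-13 points.

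**2. Leaving clinician out.** Let m be the mean discussion rate and s the between-clinician SD of that rate. With near-complete balance within clinician, the standard error is inflated by √[m(1−m) / (m(1−m) − s²)]. At m = 0.45, m(1−m) = 0.2475.
- s = 0.15: √(0.2475/0.2250) = 1.049. Null rejection is 2[1 − Φ(1.96 × 1.049)] = 4.0%.
- s = 0.20: √(0.2475/0.2075) = 1.092. Null rejection is 2[1 − Φ(1.96 × 1.092)] = 3.2%.

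Simulation under assumed clinician variation gave 2.5-4.1%, with about 3-9 points of power lost. With no clinician variation, fixed clinician effects cost little or nothing.

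**3. What dementia status could add.** Let q be prevalence and g the difference in discussion rate between patients with and without dementia. Assume 30% discussion with usual care and 60% with CHEC, so the within-arm variance is (0.21 + 0.24)/2 = 0.225. Then R² = q(1−q)g²/0.225, and the ratio of adjusted to unadjusted standard error is √[(1−R²) × 58/57].

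| g | R² (q = 0.3; 0.5) | SE ratio (q = 0.3; 0.5) |
|---|---|---|
| 10 points | 0.009; 0.011 | 1.004; 1.003 |
| 20 points | 0.037; 0.044 | 0.990; 0.986 |
| 30 points | 0.084; 0.100 | 0.965; 0.957 |
| 40 points | 0.149; 0.178 | 0.930; 0.915 |

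Reference power is 0.69 on the normal approximation. It becomes 0.68-0.69 at 10 points, 0.70 at 20, 0.72-0.73 at 30 and 0.75-0.76 at 40.

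**4. Chance imbalance.** The exact binomial probability that the arms differ by 6 or more of 30 is 12.0%, 14.7% and 15.5% at prevalences of 30%, 40% and 50%. A 20-point imbalance shifts the unadjusted arm difference by 0.20 × g, which is 4-6 points for g = 20-30 points.

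**The case against.** **The stronger reading on dementia.** A reader might infer that the plan collects dementia status and then excludes it, so that Hypothesis 5 certainly loses precision. The documents do not support this. Both covariate lists are examples, and the model is to account for unspecified pre-intervention measures, so dementia is not pre-specified but is not ruled out. Section 2 speaks of caregiver factors being influential where there is dementia; it does not say that dementia predicts discussion of needs at a visit. It names physical health alongside cognition. The abstraction lists diseases and diagnoses, not dementia by name. Dementia is therefore a reasonable choice rather than one the protocol compels.

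**Selection.** Section 8 does not say that the most favourable model will be kept. The 7-10% is what the wording permits, not a forecast.

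**The written model.** With complete pre- and post-visit data, a fixed main effect for dementia, clinician or any other covariate would cancel from the group-by-time contrast, and none of the effects above would arise. This is correct. However, the schedule of assessments shows one recorded visit per dyad. If discussion is scored from that recording, there is no pre-visit value and the comparison reduces to a single time point, as computed here. That mismatch between outcome and model is a separate matter and arguably a larger one.

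**Pilot status.** Feasibility and acceptability are the primary objective, impact is preliminary, and no alpha is stated. This limits the urgency. But Section 8 itself calls discussion of needs the primary outcome variable, and the spread of estimates across models matters whether or not a test is made.

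**Conclusion.** The point holds in a limited form. Section 8 leaves the Hypothesis 5 model open and does not name the randomisation stratum. Keeping the best of the 16 available models would raise null rejection from about 5% to about 7-10%, or roughly 1.4 to 2 times. Omitting clinician works in the other direction: it is conservative and costs some power if clinicians differ, and is harmless if they do not. Adding dementia status gives no gain at a 10-point difference in discussion rate and cuts the standard error by about 3-8% at 30-40 points. All of these sizes rest on assumed rates, prevalence, clinician variation and a single-visit linear analysis. The covariate-selection simulations ignore clinician blocks and dropout. The absence of a fixed model and of clinician can be read directly from the text and needs no assumption.

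**What to change.** Replace the covariate sentence in Section 8 before any visit recording is scored. Name one primary model for Hypothesis 5 with arm, clinician (as a fixed or random effect) and chart-recorded dementia or cognitive-impairment diagnosis (yes/no). Add that diagnosis as a named item in the pre-visit chart abstraction. State that models with caregiver or patient age, gender or race are sensitivity analyses and will be labelled as such.

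No new data source is needed. The cost is one degree of freedom for dementia and up to nine for clinician if 10 clinicians enter as fixed effects; a random effect uses fewer. Diagnoses may be under-recorded in the chart, which would shrink any gain from that covariate.

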9.1. Adverse Event Definition

An adverse event (also referred to as an adverse experience) can be any unfavorable and unintended sign (e.g., an abnormal laboratory finding), symptom, or disease temporally associated with the use of a drug, and does not imply any judgment about causality. An adverse event can arise with any use of the drug (e.g., off-label use, use in combination with another drug) and with any route of administration, formulation, or dose, including an overdose.

9.1.1 Adverse Event Characteristics and Related Attributions

CTCAE term (AE description) and grade: The descriptions and grading scales found in the revised NCI Common Terminology Criteria for Adverse Events (CTCAE) version 4.0 will be utilized for AE reporting. A copy of the CTCAE version 4.0 can be downloaded from the CTEP web site (<http://ctep.cancer.gov>).

- Attribution of the AE:
 - Definite – The AE is *clearly related* to the study treatment.
 - Probable – The AE is *likely related* to the study treatment.
 - Possible – The AE *may be related* to the study treatment.
 - Unlikely – The AE is *doubtfully related* to the study treatment.
 - Unrelated – The AE is *clearly NOT related* to the study treatment.

9.1.2 Recording of Adverse Events

All adverse events will be recorded on a subject specific AE log. The AE log will be maintained by the research staff and kept in the subject's research chart.

9.1.3 Reporting of AE to WCM IRB

All AEs occurring on this study will be reported to the IRB according to the IRB policy, which can be accessed via the following link:

http://researchintegrity.weill.cornell.edu/forms_and_policies/forms/Immediate_Report_Policy.pdf.

9.1.4 Reporting Events to Participants

Not applicable

9.1.5 Events of Special Interest

Not applicable

9.1.6 Reporting of Pregnancy

Not applicable

10. Unanticipated Problems Involving Risks to Subjects or *Others*
Not applicable

**10.1 Definition of Unanticipated Problems Involving Risks to Subjects or *Others*
(UPIRTSO)**
Not applicable

10.1.1 Unanticipated Problem Reporting
Not applicable
